12.3.1 Number of subjects to be enrolled

Number to be enrolled:

Phase 1b: minimum of 9, maximum of 12

Phase 2: 6 subjects from MTD level in Phase 1b and an additional 29 subjects for a projected sample size of 35.

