5 OVERALL DESIGN AND TREATMENT PLAN

5.1 Phase 1b Dose Escalation Plan

This Phase Ib dose escalation study will evaluate entrectinib in combination with PAC-1 in subjects with metastatic uveal melanoma. Entrectinib will be taken orally on Days 1-28 of each 28 day cycle and PAC-1 will be taken orally on Days 1-21 of each 28-day cycle (see exception for Cycle 1 below), and response to treatment will be evaluated after every 2 cycles. Treatment will continue until disease progression (based on RECIST 1.1 criteria), unacceptable toxicity, subject withdrawal of informed consent, or subject death either from progression of disease, the therapy itself, or from other causes. Subjects who withdrew from study treatment, have progressive disease, or unacceptable toxicities will be followed for survival every 2 months for 12 months from start of study treatment, then every 3 months for up to 24 months.

Pharmacokinetic (PK) and pharmacodynamic (PD) assay for PAC-1 will be performed during Days 1 and 21 of Cycle 1. PAC-1 will be given on Day 1 of Cycle 1, withheld on Day 2 and Day 3 of Cycle 1 then reinitiated on Day 4 of Cycle 1 to continue to Day 21 of the 28-day cycle. For

each successive cycle, PAC-1 therapy will be initiated on Day 1 and continue to Day 21 of the 28-day cycle.

Pharmacokinetic and pharmacodynamic assay for entrectinib will be performed during Days 3 and 21 of Cycle 1. Entrectinib therapy will be withheld on Day 1 and Day 2 of Cycle 1, initiated on Day 3 of Cycle 1 and continue for the remainder of the cycle. For each successive cycle, entrectinib will be initiated on Day 1 and continue for the remainder of the 28 day cycle.

Cycle 1 of Treatment (Cycle = 28 Days)

Drug	Dose	Route	Cycle 1 Frequency
PAC-1	TBD	Orally	Day 1 then Day 4 to Day 21; HELD Day 2 and Day 3
Entrectinib	600 mg		Day 3 to Day 28; HELD Day 1 and Day 2

Cycle 2 and Subsequent (Cycle = 28 Days)

Drug	Dose	Route	Frequency
PAC-1	TBD	Orally	Day 1 to Day 21
Entrectinib	600 mg		Day 1 to Day 28

Study Treatment Dose Levels

Dose Level*	PAC-1 Dose (mg, orally)	Entrectinib (mg, orally)	# of Subjects [^]
-1	625 daily	400 daily	3-6
1 (starting)	625 daily	600 daily	3-6
2	750 daily	600 daily	3-6

*Pharmacokinetics analysis will be performed at both dose levels during Cycle 1.

[^]MTD cohort will be initially expanded to 6 patients, and if no DLT move to Phase 2 study.

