5.1.1 Dose Escalation Rules and MTD Definition

- Three subjects will initially be enrolled at dose level 1. If none of the 3 subjects experience a dose limiting toxicity (DLT) during the first cycle of therapy, three subjects will be enrolled at dose level 2. If all subjects in dose level 2 complete the first cycle of therapy without DLT, 3 more subjects will be enrolled into dose level 2 to ensure only 0-1 of 6 subjects have a DLT. There will be no further escalation beyond dose level 2.
- Alternatively, if 1 of the first 3 subjects within a dose level cohort experiences a DLT, the cohort will be expanded to 6 subjects. If this happens within dose level 1 and only 1 of the total 6 subjects in dose level 1 experience DLT, the study will proceed to dose level 2. If 2 or more of 6 subjects in a cohort experience DLTs, or 2 subjects within a cohort of 3 subjects experience DLT during the first cycle of therapy (>33% of subjects experiencing DLT), the MTD is exceeded. If this occurs at dose level 1, additional subjects will be accrued to dose level -1. If this occurs at dose level 2, 3 additional subjects will be

enrolled into dose level 1, unless there have been 6 subjects already enrolled into dose level 1.

- The MTD of PAC-1 in combination with entrectinib is the highest tested dose of PAC-1 combined with entrectinib with DLT rate of less than 33% in the first cycle of therapy (i.e., ≤ 1 out of 6 subjects with DLT). That dose will be recommended for the Phase 2 study.
- At the discretion of the sponsor-investigator, a lower Phase 2 dose may be recommended if other toxicity emerges during the Phase 1b study which does not meet DLT criteria but limits the dose that can be administered cumulatively.

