12. STATISTICAL CONSIDERATIONS

12.1 Study Design

This is a single arm study.

Phase 1b: The primary objective of the Phase Ib dose escalation cohort study is to establish the MTD of PAC-1 in combination with entrectinib in subjects with metastatic uveal melanoma. A standard “3+3” design will be used to establish the MTD. PAC-1 (PO) will be given daily on Days 1 through 21 of each cycle. Entrectinib (PO) will be given daily on Days 1 through 28 of each cycle. Each cycle will equal 28 days. Response will be evaluated after every 2 cycles. Treatment will continue until disease progression based on RECIST criteria or intolerable toxicity.

Phase 2: The primary objective of the Phase II trial is to estimate 3 months PFS using RECIST v1.1 in subjects with metastatic uveal melanoma treated with PAC-1 in combination with entrectinib. PAC-1 (PO) will be given daily on Days 1 through 21 of each cycle. Entrectinib (PO) will be given daily on Days 1 through 28 of each cycle. Each cycle will equal 28 days. Response will be evaluated after every 2 cycles. Treatment will continue until disease progression based on RECIST criteria or intolerable toxicity. Subjects who voluntarily stop the study, have progressive disease, or unacceptable toxicities will be followed for survival every 2 months for 12 months from start of study treatment, then every 3 months for up to 24 months.

Correlative research analyses include examining the relationship between procaspase 3 expression in archived tumor tissue to degree of clinical response.

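### The Phase 1b maximum of 12 in section 12.3.1 leaves out dose level -1; the escalation rules in section 5.1.1 can enrol up to 18

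*Combined protocol and SAP*

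**What the plan says.** Section 12.3.1 states the range without qualification: "Phase 1b: minimum of 9, maximum of 12". Section 12.1 names the method: "A standard “3+3” design will be used to establish the MTD".

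The dose tables in the Phase 1b schema and section 5.1 list levels -1, 1 and 2, each with 3 to 6 subjects. Levels 1 and 2 use entrectinib 600 mg; level -1 uses 400 mg.

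Section 5.1.1 sets the path:

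- Start: "Three subjects will initially be enrolled at dose level 1".
- Level 2 after 0/3 DLTs: "3 more subjects will be enrolled into dose level 2 to ensure only 0-1 of 6 subjects have a DLT".
- Either level after one DLT: "if 1 of the first 3 subjects within a dose level cohort experiences a DLT, the cohort will be expanded to 6 subjects".
- A level is exceeded at 2 DLTs among 3 subjects, or at 2 or more among 6.
- Level 2 exceeded: "If this occurs at dose level 2, 3 additional subjects will be" enrolled at level 1, unless 6 are already there.
- Level 1 exceeded: "If this occurs at dose level 1, additional subjects will be accrued to dose level -1".

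Section 5.1.2 requires at least 6 subjects in total at the MTD. Two other places describe Phase 1b more narrowly. Section 10.2.5 mentions only 600 mg entrectinib for both phases, and section 12.5.1 defines the MTD as a PAC-1 dose given with 600 mg entrectinib. A footnote to the section 5.1 table also speaks of PK at both levels, although the table has three.

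**The concern.** A stated maximum is a bound, so every path through the rules should respect it. Twelve equals two levels of six, yet the dose table has three levels and section 5.1.1 sends subjects to the third. The rule for opening level -1 makes no exception for a level 1 cohort that was refilled after level 2 failed.

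What is at stake is planning and consistency. If toxicity forces de-escalation, one section gives a Phase 1b count that another section tells sites to exceed. The mismatch also shows that the document has not settled whether level -1 belongs to Phase 1b for counting purposes and for defining the MTD.

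**Working it through.** **Inputs.** Cohort sizes come from the section 5.1 table, transitions from section 5.1.1, and the minimum MTD cohort from section 5.1.2. DL means dose level.

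**The plan's figures.** Counting DL1 and DL2 only, the maximum is 6 + 6 = 12, as stated. The planned path is 3 at DL1 plus 6 at DL2 = 9, the stated minimum.

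**All paths with DL-1 included.**

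| Path | DL1 | DL2 | DL-1 | Total |
|---|---|---|---|---|
| DL1 0/3; DL2 at most 1/6 | 3 | 6 | 0 | 9 |
| DL1 1/6; DL2 run, either outcome | 6 | 3 or 6 | 0 | 9 or 12 |
| DL1 0/3; DL2 exceeded; DL1 refilled, at most 1/6 | 6 | 3 or 6 | 0 | 9 or 12 |
| DL1 exceeded at first pass; DL-1 opened | 3 or 6 | 0 | 3 or 6 | 6, 9 or 12 |
| DL1 0/3; DL2 exceeded; DL1 refilled and exceeded; DL-1 opened | 6 | 3 or 6 | 3 or 6 | 12, 15 or 18 |

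Only the last row passes 12. It reaches 6 + 6 + 6 = 18 when DL2 and DL-1 both fill. If DL2 fails after 3 subjects, it reaches at most 6 + 3 + 6 = 15.

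The total of 6 is DL1 stopped at 3 plus DL-1 stopped at 3. No MTD is declared on that path. Every path that declares an MTD has at least 9.

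**Probability of the last row exceeding 12.** The documents give no DLT rates, so p₋₁, p₁ and p₂ are assumed for DL-1, DL1 and DL2. Let:

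- a = (1−p₁)³, DL1 clears at 0/3
- f₃ = 3p₂²(1−p₂) + p₂³, DL2 exceeded after 3 subjects
- f₆ = 1 − f₃ − [(1−p₂)⁶ + 6p₂(1−p₂)⁵], DL2 exceeded after 6
- c = 3p₁²(1−p₁) + p₁³, at least 2 DLTs in the 3 added at DL1
- h = 3p₋₁²(1−p₋₁) + p₋₁³, DL-1 stops at 3; g = 1 − h, DL-1 fills to 6

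Then P(18) = a·f₆·c·g and P(15) = a·c·(f₆·h + f₃·g). Ending at 6 has probability c·h, because c is also the chance of at least 2 DLTs in the first 3 at DL1.

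For rates of 15/25/35% at DL-1/DL1/DL2: a = 0.4219, f₃ = 0.2817, f₆ = 0.3992, c = 0.1562, g = 0.9393, h = 0.0607.

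- P(18) = 0.4219 × 0.3992 × 0.1562 × 0.9393 = 0.025
- P(15) = 0.4219 × 0.1562 × (0.3992 × 0.0607 + 0.2817 × 0.9393) = 0.019
- P(above 12) = 0.044

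| Assumed DLT rates, DL-1/DL1/DL2 | P(above 12) | P(18) | P(6) |
|---|---|---|---|
| 10/15/25% | 1.7% | 1.1% | 0.2% |
| 15/25/35% | 4.4% | 2.5% | 0.9% |
| 20/33/45% | 6.1% | 2.8% | 2.7% |

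**The case against.** The best defence is that 12 is right for one of the document's two descriptions of Phase 1b. Sections 10.2.5 and 12.5.1 and the PK footnote treat Phase 1b as the two 600 mg levels, and for those 6 + 6 = 12. This stands as an explanation of the figure. It does not remove the conflict, because section 5.1.1 still requires accrual to level -1 and the tables list that level within Phase 1b. It does mean that changing 12 to 18 alone would leave section 12.5.1 unreconciled.

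It is also fair that the path is improbable and leaves the Phase 2 hypothesis, sample size and analysis untouched.

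Two stronger readings are tempting, and the documents support neither.

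- A reader might add the 29 further Phase 2 subjects to 18 and conclude that the study could reach 47. Every path above 12 has both 600 mg levels exceeded and only the 400 mg level left. Section 5.2 specifies Phase 2 at 600 mg, and section 12.5.1 ties the MTD to 600 mg. No Phase 2 described in the protocol follows such a path, so the sum joins two incompatible branches.
- A reader might infer that enrolment must halt at 12 for an amendment, or that an IRB ceiling would be breached. Section 12.3.1 lists numbers to be enrolled. Nothing in the protocol makes 12 a stopping limit or mentions an IRB enrolment ceiling. Nor is 12 always reached when level -1 opens: if level 2 fails after 3 subjects, level -1 opens at 3 + 3 + 3 = 9.

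**Conclusion.** The maximum in section 12.3.1 is inconsistent with sections 5.1 and 5.1.1. Under the rules as written, Phase 1b can total 6, 9, 12, 15 or 18; 12 is the maximum only if level -1 is not opened after level 2. The stated minimum of 9 holds only if an MTD is declared.

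The path counts rest on the rules alone, with 6 as the upper size at level -1 taken from the dose tables. Any subjects replaced under section 5.6.3 would be additional. The 2% to 6% chance of exceeding 12 rests on assumed DLT rates. This is a minor planning inconsistency with no effect on the Phase 2 inference.

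**What to change.** Reconcile sections 5.1, 5.1.1, 12.3.1 and 12.5.1, with section 10.2.5 checked against the result, so that the status of level -1 is the same throughout. Then do one of the following in section 12.3.1:

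- state a maximum of 18 (6 at each of three levels), noting that 12 holds when level -1 is not opened after level 2; or
- keep 12 and state that it excludes level -1.

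In the same line, say that the minimum of 9 assumes an MTD is declared and that the rules can end at 6 without one. Do not carry 18 into the study total. The sponsor should settle, and the protocol should say, what follows if only level -1 remains.

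The cost is a few lines of text and one decision by the sponsor. Correcting the count changes neither expected enrolment nor the Phase 2 sample size.

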The primary objective of the Phase 2 Study is to estimate 3 month progression-free survival (PFS) using RECIST v1.1 in subjects with metastatic uveal melanoma.

Phase II

Entrectinib dosed at 600 mg once daily; PAC-1 dosed once daily at RP2D from Phase 1b study.

ABBREVIATIONS

Abbreviation	Definition
AE	adverse event
ANC	absolute neutrophil count
ALK	anaplastic lymphoma kinase
ALT	alanine aminotransferase
ASCO	American Society of Clinical Oncology
AST	aspartate aminotransferase
BUN	blood urea nitrogen
CBC	complete blood count
cm	centimeter
CMP	comprehensive metabolic panel
CNS	central nervous system
CR	complete response
CT	computed tomography
CTCAE	(NCI) Common Terminology Criteria for Adverse Events
CTEP	Cancer Therapy Evaluation Program
CYP	cytochrome P450
dL	deciliter
DOOR	duration of response
ECG	electrocardiogram
ECOG	Eastern Cooperative Oncology Group
ERK	extracellular signal-regulated kinase
FDA	Food and Drug Administration
FDAAA	Food and Drug Administration Amendments Act
FDAMA	Food and Drug Administration Modernization Act
GFR	glomerular filtration rate
h	hour
Hgb	hemoglobin
IB	Investigator's Brochure
IND	Investigational New Drug
IRB	institutional review board
kg	kilogram
lbs	pounds
LDH	lactic dehydrogenase
mg	milligram
min	minute
mL	milliliter
mm ³	cubic millimeters

MRI	magnetic resonance imaging
MTD	maximum tolerated dose
NSCLC	non-small cell lung cancer
NTRK	neurotrophic tyrosine kinase
ORR	overall response rate
OS	overall survival
PAC-1	first procaspase-activating compound
PFS	progression-free survival
PK	pharmacokinetics
PR	partial response
PT	prothrombin time
PTT	partial thromboplastin time
RECIST	Response Evaluation Criteria in Solid Tumor
ROS1	ROS proto-oncogene 1
SAE	serious adverse event
SDEA	Safety Data Exchange Agreement
TKI	tyrosine kinase inhibitor
Trk	tropomyosin-related kinase
ULN	upper limit of normal
US	United States
WHO	World Health Organization
WOCP	women of childbearing potential
wt	weight

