5.3.2 PAC-1

In Phase 1b, PAC-1 (PO) will be dosed at 625 or 750 mg daily in the morning on Days 1-21 of each 28 day cycle (for exception in cycle 1, see below). The dose which is determined to be the MTD will be taken in the morning on Days 1-21 of the cycle in Phase 2.

During Cycle 1 for each dose level, subjects will be instructed to administer their daily dose at the same approximate time (+/- 1 hour) each morning. Subsequent cycles must meet the criteria found in section 6.1. The study drug will be administered in the morning and on an empty stomach with the patient remaining NPO (nothing by mouth), except for water and prescribed medications, for 2 hours before and 1 hour after each dose. Patients will be instructed to take each oral dose of PAC-1 with 8 ounces of water (1 cup, 240 mL).

For Cycle 1, PAC-1 will be given on Day 1 and withheld on Days 2 and 3. The dose on these days are being held in order to determine the PK of single-agent entrectinib on Day 3 of the cycle. PAC-1 treatment will be re-initiated on Day 4 and continue to Day 21 of the 28-day cycle. Administration of PAC-1 on Days 1 and 21 of Cycle 1 will occur in the morning. Information on the time and number of PAC-1 doses received for the 96 hours prior to the dose on Day 21 will be obtained from subjects.

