12.3 Sample Size and Accrual

Previous studies in the target population identified PFS at 3 months of 38%.⁶ We hypothesize PFS at 3 months of 65%. Controlling for a probability of Type I error at 0.05 (one-sided), our sample size in Phase 2 is estimated to be 32 to ensure 90% statistical power in successfully detecting an alternative PFS rate at 3 months of 0.65, compared to a null rate of 0.38. With 3 additional patients to account for a 10% drop off rate, sample size for phase 2 study will be 35. Sample size analyses were conducted using the PASS software (NCSS, Kaysville, Utah, USA). With phase 1b study component, the study will need to have 3 subjects from Dose Level 1 of Phase 1b + 6 subjects from Dose Level 2 of Phase 1b (and carried over to Phase 2 study). The total number of subjects for the study is 38.

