12.5 Data Analysis Plans

12.5.1 Analysis Plans for Primary Endpoint

Phase Ib Analysis of Primary Endpoint

The primary endpoint is determination of the MTD of PAC-1 in combination with entrectinib. The MTD will be defined as the highest explored dose of PAC-1 combined with 600 mg of entrectinib at which ≤ 1 out of 6 subjects have experienced a DLT within the first cycle of therapy. That dose will be recommended for the Phase 2 study (i.e., will be declared the RP2D). At the discretion of the sponsor-investigator, a lower Phase 2 dose may be recommended if other toxicity emerges during the Phase Ib study which does not meet DLT criteria but limits the dose that can be administered cumulatively.

Phase II Analysis of Primary Endpoint

The primary endpoint is determination of the activity of the combination of PAC-1 and entrectinib for treatment of metastatic uveal melanoma, as assessed by 3 months PFS based on RECIST v1.1. Median PFS times will be computed with associated 95% confidence intervals. Kaplan-Meier curves will be plotted.

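### The Phase 1b subjects counted in the Phase 2 sample are defined by the MTD level or Dose Level 2, not by the RP2D, so the primary rate would mix doses if the plan's lower-dose option is used

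*Combined protocol and SAP*

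**What the plan says.** Section 12.3.1 gives the make-up of the efficacy sample: "Phase 2: 6 subjects from MTD level in Phase 1b and an additional 29 subjects for a projected sample size of 35". Section 12.3 and the synopsis describe the same six as coming from Dose Level 2. Neither place attaches a condition.

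Section 12.5.1 makes the MTD the RP2D by default, then adds that at the sponsor-investigator's discretion "a lower Phase 2 dose may be recommended if other toxicity emerges during the Phase Ib study which does not meet DLT criteria". Section 5.1.1 contains the same option. The Phase 2 schema has "PAC-1 dosed once daily at RP2D from Phase 1b study", and 5.2 also treats at the recommended Phase 2 dose. Section 5.3.2 says something different: "The dose which is determined to be the MTD will be taken in the morning on Days 1-21 of the cycle in Phase 2".

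The efficacy set in 12.4.2 depends on measurable disease, one cycle of therapy and re-evaluation. The safety set in 12.4.1 depends on one dose of trial drug. Neither refers to dose level or study phase. No section says what happens to the carried-over six if the RP2D is below the MTD.

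**The concern.** Phase 2 asks about activity at the dose recommended for Phase 2. The plan allows that dose to differ from the MTD, yet the subjects counted in advance are identified by the MTD level, or by a fixed dose level. Suppose Level 2 is the MTD and Level 1 is chosen as the RP2D. The written rule then counts six subjects assigned to the dose that was set aside, and omits the three to six subjects assigned to the dose under study. The 3-month PFS rate would no longer be an estimate for the RP2D. The Phase 2 response and adverse event proportions could be mixed in the same way.

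The Dose Level 2 wording also fails without the discretionary option. If Level 2 exceeds the MTD, 5.1.1 goes back to Level 1, but 12.3 and the synopsis still name Level 2 as the source of the carry-over.

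This is a single-arm, open study, and the Phase 1b subjects' outcomes may be known when the Phase 2 dose is settled. The rule on whom to count should therefore be fixed beforehand.

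**Working it through.** **1. The plan's own figure.** Inputs from 12.3: one-sided type I error 0.05, null 3-month PFS rate 0.38, alternative 0.65, and "our sample size in Phase 2 is estimated to be 32 to ensure 90% statistical power". In an exact one-sample binomial test, the cutoff r is the smallest count with P(X ≥ r | n, 0.38) ≤ 0.05, and power is P(X ≥ r | n, 0.65). For n = 32, r = 18, the exact alpha is 0.027 and the power 0.888. The one-sided normal approximation with continuity correction gives 30.9, so 31. The stated 32 is reasonable. With 3 added for drop-off, 32 + 3 = 35 = 6 + 29.

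**2. Counts by branch.**

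| Branch | Counted under 12.3 / 12.3.1 | Phase 1b subjects at the RP2D |
|---|---|---|
| MTD = Level 2 = RP2D (default) | 6 at Level 2 | the same 6 |
| MTD = Level 2, RP2D = Level 1 | 6 at Level 2 | 3 to 6 at Level 1, not counted |
| MTD = Level 1 = RP2D | 12.3.1: 6 at Level 1; 12.3: 6 at Level 2 | 6 at Level 1 |
| RP2D is a dose given to no one in Phase 1b | 6 at the MTD level | 0 |

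The last branch is possible because 5.1.1 opens Level -1 only if Level 1 exceeds the MTD, and because the lower dose is not limited to a tested level. Where mixing occurs, the share is 6/35 = 17.1%.

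**3. Possible effect on the primary rate.** The documents give no dose-specific PFS rates and 12.5.1 states no test or cutoff, so both are assumptions here. For n = 35 the exact cutoff is 19, with alpha 0.037 and power 0.932 if all subjects share one rate. Let the 29 new subjects have rate q and the six have rate p. The expected pooled rate is (29q + 6p)/35. The chance of 19 or more successes comes from convolving Binomial(29, q) with Binomial(6, p).

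| q (RP2D) | p (the six) | Pooled rate | P(19 or more of 35) |
|---|---|---|---|
| 0.38 | 0.38 | 0.380 | 0.037 |
| 0.38 | 0.42 | 0.387 | 0.044 |
| 0.38 | 0.45 | 0.392 | 0.050 |
| 0.38 | 0.50 | 0.401 | 0.062 |
| 0.38 | 0.65 | 0.426 | 0.106 |
| 0.65 | 0.65 | 0.650 | 0.932 |
| 0.65 | 0.50 | 0.624 | 0.880 |

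For example, (29 × 0.38 + 6 × 0.65)/35 = 14.92/35 = 0.426.

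**4. Sample if only RP2D subjects are carried over.** There are 29 new subjects plus 0 to 6, so 29 to 35 enrolled.

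| Evaluable | Cutoff | Exact alpha | Power at 0.65 |
|---|---|---|---|
| 26 | 15 | 0.033 | 0.838 |
| 29 | 16 | 0.045 | 0.902 |
| 32 | 18 | 0.027 | 0.888 |
| 35 | 19 | 0.037 | 0.932 |

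Power does not rise steadily because the cutoff moves in whole subjects. The row for 26 is 29 enrolled less 10% (29 × 0.9 = 26.1).

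**The case against.** The best reply is that 12.3 and 12.3.1 are accrual projections along the expected path: 3 subjects at Level 1, 6 at Level 2, and the MTD declared as the RP2D. On that path no assigned doses are mixed. A reader might infer that the plan deliberately keeps the six in the Phase 2 sample even when a lower dose is chosen. No section says so. What stands is narrower: the wording is unconditional, and no other rule covers the lower-dose case.

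A reader might also infer that the type I error would roughly double. The documents do not support that. The cutoff is assumed, and 0.106 needs no effect at the RP2D together with the full hypothesised rate at the other dose. In the Level 2 to Level 1 branch the levels differ only in PAC-1, 750 against 625 mg. With the six at 0.45, the rate is still about 0.050. With 32 evaluable and a cutoff of 18, even 0.50 gives 0.048. If both doses have the same rate, nothing changes.

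Section 6.2.1 also allows dose reductions, so doses received will vary within any assigned level. That is true, but the estimate is by assigned dose, and reductions during treatment do not explain counting subjects who started on a different dose.

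Finally, the safety set in 12.4.1 has no dose or phase restriction, so mixed adverse event proportions do not come from 12.3.1 alone. This is correct, and it means that editing 12.3.1 would not by itself separate the safety results.

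**Conclusion.** The counting rule does not work in a branch that the plan provides for twice, in 5.1.1 and 12.5.1. In that branch 6 of 35 subjects (17%) in the primary rate were assigned a dose other than the RP2D, and Phase 1b subjects at the RP2D are not counted. The Dose Level 2 wording in 12.3 and the synopsis also fails if the MTD is Level 1. In the default case there is no problem, and the sample-size calculation itself is sound.

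The direction and size of any bias rest on a dose-response that the documents do not give. Over the assumed range, the false-positive rate runs from 0.037 to 0.106, and power could fall from 0.932 to 0.880 if the six do worse than the RP2D subjects. The point should be corrected because the change is specific and inexpensive, not because a large bias has been shown. Sections 5.3.2, 5.1.1, 5.2 and 12.5.1 must also be reconciled on which dose Phase 2 uses. This review takes no position on which is right.

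**What to change.** - In the synopsis, 12.3 and 12.3.1, replace the references to Dose Level 2 and the MTD level with: Phase 1b subjects treated at the RP2D dose pair. The word pair matters because Level -1 differs from Level 1 in entrectinib, not in PAC-1.
- Put the same condition in 12.4 and 12.5, so that the Phase 2 efficacy and adverse event proportions are for RP2D subjects and those for other dose levels are reported separately.
- State the resulting sample and power: 29 new plus 0 to 6 carried over, so 29 to 35 enrolled. If all are evaluable, exact power is about 0.90 at 29, 0.89 at 32 and 0.93 at 35. It is about 0.84 if 29 enrolled leave 26 evaluable.
- Reconcile 5.3.2 with 5.1.1, 5.2 and 12.5.1.

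Cost: in the default case, wording only. In the lower-dose branch the drop-off allowance shrinks or disappears. A reader might infer that the sample always stays at 32 to 35, but that holds only when Level 2 is the MTD and Level 1 is the RP2D. Even then, 32 enrolled leaves about 29 evaluable after 10% loss (32 × 0.9 = 28.8). Keeping 35 subjects at the RP2D would take up to 6 more new subjects. For example, with 3 subjects at Level 1 carried over, 32 new subjects are needed, and the study total becomes 3 + 6 + 32 = 41 instead of 38.
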